6.2 Subject Characteristics

All subject characteristics data will be listed by subject, and summarized for the ITT population, except as noted otherwise.

6.2.1 Subject Disposition

Subject disposition will be presented for all subjects by parent study treatment group and overall for the ITT population. Disposition information that will be summarized will include number of subjects who completed the study, number who withdrew prematurely, and reasons for withdrawal.

The number and percent of subjects in each of the following categories will be presented.

- Safety population
- Subjects completing weeks 16 and 52
- Subjects discontinued from the study and by reason of discontinuation.

6.2.2 Protocol Deviations

Subjects with major protocol deviations will be identified by the medical or clinical data review prior to database lock. The deviations will be summarized by parent treatment group and overall based on the safety population. The summary will be grouped into different categories of violations such as below as example:

- Inclusion/Exclusion Criteria Deviations
- Non-compliance with study procedures
- Inappropriate intake of prohibited medications
- Poor compliance with study medications
- Lost to follow-up
- Administrative decision of investigator or sponsor

Multiple deviations can occur in the same subject and thus a subject may be counted in more than one deviation category.

A listing of subjects with major deviations will be presented.

All decisions regarding major deviations will be discussed and agreed upon with the sponsor prior to the database lock.

6.2.3 Demographics and Background Baseline Characteristics

6.2.3.1 *Subject Demographics data.*

Demographics data is collected at time of screening after informed consent is obtained and migrated from the parent study (please refer to Appendix for details). Demographics variables will be summarized descriptively for ITT subjects by parent study treatment group and overall and will at least include the following variables:

- Age at screening as continuous variable [Years]
- Sex
- Race
- Ethnicity
- Height
- Weight
- Smoking status and alcohol consumption
- BMI

6.2.4 Treatment Exposure and Drug Accountability

6.2.4.1 *Treatment Exposure*

Exposure will be summarized for the SAF population. Subjects are instructed to bring their study medication and all empty packaging to the clinic visit. Cumulative treatment exposure per subject will be calculated as sum of all dosage of treatment consumed. Time on treatment (in days) will be calculated per subject as the number of days of study medication intake during the trial. This will be calculated as:

Date of last study medication administration – Date of first study medication administration + 1.

Dosing data will be presented descriptively by parent study treatment group and overall and also presented as subject data listing for the Safety population.

In addition, treatment duration (RHB-104 or Placebo) of combined parent study and current study will be descriptively summarized by parent study treatment group. Combined treatment duration in weeks will also be categorically summarized displaying the number and percentage of patients with treatment duration by every 10 weeks and by parent study treatment group.

6.2.4.2 *Accountability/Compliance*

Drug compliance will depend upon capsule counts at each visit. Subjects are instructed to bring their study medication and all empty packages to each clinic visit. Compliance will be assessed by capsule counts recorded by each site for each subject. The details of medication used will be recorded and reconciled against expected medication use. Compliance will be calculated as the reported medication used by subject as percentage (%) of expected usage. Summary descriptive statistics will be presented for the number and proportion of subjects non-compliant (< 80% compliant) for safety population.

Version 1.0, 23 Dec 2019

Extent of compliance of each subject data will be presented in subject listing for the SAF population.

6.2.5 Physical Examination

Complete physical examination is performed at screening and includes each subject's major body systems: general appearance, head/eyes/ears/nose/throat, neck, lungs, heart, abdomen, genitourinary, extremities, neurological, skin, and lymphatics and other. Results (normal, abnormal and clinically significant abnormal and not clinically significant) will be tabulated for each body system with the number and percentage of subjects.

Number of percent of subjects with significant change in physical examination from previous visit at baseline and subsequent post baseline visits will be summarized.

6.2.6 Medical History (excluding Crohn's disease)

6.2.6.1 Medical History (excluding Crohn's disease)

Pre-existing medical conditions are recorded at screening on the medical history eCRF per subject data migration from the parent study (please refer to Appendix for details). For each subject, medical history data will be presented in a data listing.

6.2.6.2 Crohn's Disease History

Crohn's disease history is recorded at screening on the history eCRF per subject data migration from the parent study (please refer to Appendix for details). Data including steroid status (steroid-refractory disease or steroid-dependent disease) will be presented descriptively by parent study treatment group and overall and also presented as data listing. Duration of each condition is based on the first dose of study medications administration for the current extension study.

6.2.7 Prior and Concomitant Medications and Steroids

Prior medications will be defined as medications stopped prior to Day 1 of study medication. Concomitant medications include medications taken on or after the first dose of study medication as well as medications that started prior to the first dose of study medication and continued after the first dose of study medication. The following algorithm will be used to define prior and concomitant:

The medication will be assumed to be prior medication if it cannot be definitively shown that the medication did not start or continue during the treatment period.

If the start date or stop date of a medication is partially missing, the date will be compared as far as possible with the date of the start of administration of study drug. The following approach will be taken:

- If the start date of medication is complete and occurs on or after the day of the first dose, the medication will be assumed concomitant. If the start date occurs prior to the first

- dose date but the end date is on or after the first dose date or the medication is recorded as ongoing, the medication will be considered concomitant.
- If the start day is missing but the start month and year are complete, a medication will only be excluded as being concomitant if the start month/year is before the month/year of study drug administration and if the stop date (either full date, month and year if missing day, or year if missing month and day) is before study drug administration.
 - If the start day and month are missing but the start year is complete, a medication will only be excluded as concomitant if the start year is before the year of study drug administration and if the stop date (either full date, month and year if missing day, or year if missing month and day) is before study drug administration.
 - If the start date is completely missing and the stop date is prior to first dose or completely missing, the medication will be assumed to be a prior medication.

All prior and concomitant medications recorded on CRF will be mapped to standardized terms using the World Health Organization Drug Dictionary coding system (WHO DD). The Anatomical–Therapeutic–Chemical (ATC) Classification level 2 and preferred term will be used to summarize the data by treatment group. A subject having the same medication more than once will be counted only once in the incidence table for that medication. For each ATC classification and Preferred Term the number and percentage of subjects will be displayed. Summary tables will be presented on SAF population separately for the following:

- Prior Medications Use for Crohn’s Disease
- Prior Medications Use
- Concomitant Medications Use
- Prior Biological Agents Use
- Concomitant Medications Use for Crohn’s Disease
- Prior Steroids Use
- Concomitant Steroids Use
- Concomitant Steroids Use for Crohn’s Disease
- Prior Antineoplastic, Immunosuppressive and Biologic Use
- Concomitant Antineoplastic, Immunosuppressive and Biologic Use

All prior and concomitant medications/treatments will be presented in a data listing with dose, units, frequency, route of administration, indication, start and end dates for the safety population. A separate Steroids use subject listing may be presented providing the steroid coded ATC classification, preferred term, and date.

Any concomitant procedures recorded on CRF will be presented in a data listing with procedure name, date and reason.

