2.2.1 Primary Endpoint/Variable: Remission

In general use of rescue medication is considered as treatment failure (not achieving remission or response) if there are any new use of rescue medication to treat CD or increased rescue medication dose from baseline prior to any remission or response assessment. Please refer to section 6.1.6 for more details.

The primary variable is the proportion of subjects who experienced remission at Week 16 after the initiation of open-label phase, where remission is defined as a subject having a Crohn's Disease Activity Index (CDAI) score of <150 . Subjects who have a Week 16 CDAI measurement ≥ 150 or who do not have a CDAI measurement at Week 16 will be classified as not having achieved remission at that time point. Initiation of open-label phase is the first dosing time of open-label phase and from here and after it would be reference as initiation.

The CDAI is used to assess the activity of CD; higher scores indicate more active disease.

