Completely Missing – Required to look at whether the AE is still ongoing before imputing a date and also when it started in relation to study drug. If the ongoing flag is missing then assume that AE is still present (i.e. do not impute a date). If the AE has stopped and start date is prior to first dose date then impute the 1st dose date, if it started on or after first dose date then impute a date that is after the last dose date.

(iii) TEAE definition with missing start and stop dates: If the start date of an adverse event is incomplete or missing, the event will be assumed to be a treatment-emergent adverse event (TEAE), unless the incomplete start date (month and/or year) or the stop date (complete or incomplete) clearly indicates that the event started prior to dosing. Missing/incomplete information will be reported as missing/incomplete in the subject listings.

(iv) Adverse event relationship: If the relationship for an adverse event is not recorded, it will be assumed to be treatment related in the presentation of the statistical summary of incidence results. Missing information will be reported as missing in the subject listings.

(v) Adverse event severity: If the severity of an adverse event is missing, the severity will be assumed to be severe when summarizing data. Missing information will be reported as missing in the subject listings.

(vi) Non-study medication (concomitant medications, steroids) start and stop dates: If the start and/or stop dates of non-study medication use are incomplete or missing, the use will be assumed to be concomitant, unless the incomplete date information clearly indicates that the use stopped prior to study medication dosing. Missing/incomplete information will be reported as missing/incomplete in the subject listings.

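### SAP 6.1.3(vi) and 6.2.7 set opposite defaults for medications with missing dates: a certain effect on the prior/concomitant tables, only a conditional one on remission and response

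*SAP*

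**What the plan says.** SAP 6.1.3(vi) covers non-study medications, steroids included: "If the start and/or stop dates of non-study medication use are incomplete or missing, the use will be assumed to be concomitant", with one exception, "unless the incomplete date information clearly indicates that the use stopped prior to study medication dosing".

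SAP 6.2.7 defines prior as stopped before Day 1 and concomitant as any use from first dose onward. Its algorithm then opens with a default about use while on treatment: "The medication will be assumed to be prior medication if it cannot be definitively shown that the medication did not start or continue". Bullets follow. Where only the start day is missing, "a medication will only be excluded as being concomitant if the start month/year is before the month/year of study drug administration" and the stop date also precedes dosing; the next bullet does the same for a start known only to the year. The last bullet, whose outcome is prior, begins "If the start date is completely missing and the stop date is prior to first dose or completely missing, the medication will be assumed". The section puts the classification to use in summary tables of prior and concomitant drugs, including Crohn's drugs, steroids and biologics, and in a listing.

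Treatment failure is defined elsewhere. SAP 2.2.1 counts as failure "any new use of rescue medication to treat CD or increased rescue medication dose from baseline prior to any remission or response assessment". SAP 6.1.6 repeats the idea, referring to new treatment or an increase in concomitant medication for Crohn's symptoms. Neither section cites 6.2.7, and neither says what to do when the medication date is missing. SAP 6.1.1 places the SAP above the protocol but does not rank one SAP section above another.

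**The concern.** The two defaults point in opposite directions on exactly the records for which a default is needed. A programmer cannot follow both, and the bullets of 6.2.7 do not consistently side with either. At the least, the counts of on-study steroid, Crohn's-drug and biologic use depend on which sentence is followed. These counts are how a reader of an open-label study judges what else the subjects were taking.

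The wider worry is the primary endpoint. New or increased Crohn's medication makes a subject a failure for remission and response. If an undated record were set aside as prior before the rescue check, a subject with a qualifying CDAI could stay in the numerator.

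**Working it through.** No figure in the plan depends on these rules, so the main check applies each rule to the same records.

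**Step 1. The rules side by side.** Inputs are 6.1.3(vi), the 6.2.7 lead sentence and the 6.2.7 bullets, each applied separately. Where the dates already prove on-treatment use, the 6.2.7 definition of concomitant was taken to override the lead sentence. Seven start patterns (missing; first-dose year only; first-dose month and year; an earlier month; an earlier year; full date before first dose; full date after it) were crossed with five stop patterns (missing; full date before; full date after; first-dose year only; first-dose month and year). One pairing is impossible, leaving 7 × 5 − 1 = 34.

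| Date pattern | 6.1.3(vi) | 6.2.7 lead sentence | 6.2.7 bullets | Patterns |
|---|---|---|---|---|
| Both dates missing | concomitant | prior | prior | 1 |
| Partial start; stop missing or ambiguous | concomitant | prior | concomitant | 12 |
| Start missing with ambiguous partial stop (2), or full start before dosing with stop missing or ambiguous and not marked ongoing (3) | concomitant | prior | none applies | 5 |
| Partial start in the first-dose month or year; full stop before dosing | prior | prior | concomitant | 2 |
| All others | no disagreement | no disagreement | no disagreement | 14 |

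Check: 1 + 12 + 5 + 2 + 14 = 34. These are date patterns, not records, so the tally says nothing about frequency. Three things follow:

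- With both dates missing, the lead sentence and the last bullet together oppose 6.1.3(vi).
- In 12 patterns the lead sentence is contradicted by its own section's bullets.
- In 2 patterns the bullets oppose 6.1.3(vi) in the reverse direction.

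A full start date on or after first dose is concomitant under every rule.

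**Step 2. Which default fits the data flow.** Note 3 to the visit schedule (SAP 4.1.1) keeps parent-study medications in the parent eCRF up to the day before this study's baseline. SAP Appendix I carries over only medications that are ongoing at migration. An undated entry in this study's log is therefore more likely on-study use than use that ended before dosing.

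**Step 3. Size, if the rescue flag were filtered on the class.** The exact 95% limits for x of n are the 2.5% quantile of Beta(x, n − x + 1) and the 97.5% quantile of Beta(x + 1, n − x). For 50/100 this gives 0.3983 to 0.6017, width 0.2034, which reproduces the 0.203 in SAP 6.1.7; that figure is not in dispute. Each reclassified remitter changes the rate by 1/100 = 1 point. From an assumed 30/100, with k subjects reclassified:

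| k | Rate | Exact 95% CI |
|---|---|---|
| 0 | 30% | 21.2–40.0% |
| 1 | 29% | 20.4–38.9% |
| 2 | 28% | 19.5–37.9% |
| 5 | 25% | 16.9–34.7% |

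For the Fisher comparison of parent groups (SAP 6.3.1), assuming 50 per group, 20/50 against 10/50 gives p = 0.049, and 19/50 against 10/50 gives p = 0.077. The 30%, the values of k, the group sizes and the group counts are illustrations; the documents supply none of them.

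**The case against.** The strongest reply is that the conflict stops at descriptive tables. Failure is defined by new or increased Crohn's treatment, not by the prior/concomitant class. The class could not settle it anyway. Concomitant includes baseline therapy that simply continued, and no class label places an undated drug before or after week 16. A rescue drug with a known on-study start is safe under every rule. Concomitant medications are reviewed at each visit from Baseline, and steroid status is recorded at Baseline and from week 16 on, so a rescue drug with neither date recorded is probably uncommon.

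Most of this stands. A reader might infer that the conflict by itself makes the same subject a remitter under one section and a failure under the other. The documents do not support that: it needs a programmer to filter rescue on the class, which the SAP neither requires nor forbids. Nor is 6.2.7 uniformly the lenient section, since its partial-date bullets mostly default to concomitant and in one situation are stricter than 6.1.3(vi). A deliberate choice between the rules after the data are seen is also not something the text shows; it shows only that no section takes precedence.

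Two parts of the reply fail. SAP 6.1.6 does use the term concomitant medication in its failure rule, so filtering on the class would be an understandable reading. And the lead sentence cannot be set aside as a one-word slip, because the last bullet independently gives prior when both dates are missing.

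**Conclusion.** The contradiction holds, both between 6.1.3(vi) and 6.2.7 and within 6.2.7. It is a stated rule that cannot be programmed as written, not merely missing detail. Its certain effect is on the prior and concomitant tables for steroids, Crohn's drugs and biologics. An effect on remission or response is possible but conditional. It needs an undated record that is truly new or increased Crohn's treatment before the assessment, in a subject who otherwise qualifies and has no other recorded rescue, together with a rescue flag filtered on the class. Under those conditions each subject is worth 1 point at week 16 with 100 subjects. The number of such records is not known, so no total effect can be given. This should be corrected before lock.

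**What to change.** Use one rule throughout, that of 6.1.3(vi): a medication with missing or partial dates is concomitant unless the available date parts show that use stopped before first dose. Align all three parts of 6.2.7 to it: the lead sentence, both partial-date bullets (so that a full stop date before dosing gives prior even when the start shares the first-dose month or year) and the last bullet. Changing only the lead sentence and last bullet would leave the reverse conflict in place.

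In 2.2.1 and 6.1.6, state that the failure flag is derived from new or increased Crohn's treatment and not from the prior/concomitant class. Because the single rule still cannot date an undated drug relative to week 16, add a sensitivity analysis of remission and response that counts subjects with an undated Crohn's medication once as failures and once as non-failures, and say which of the two the main table carries.

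The cost is a few sentences of SAP text, one extra sensitivity table, and some additional entries counted as concomitant in the medication tables.

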6.3 Outcome Analysis

The outcome analyses will be based on all ITT subjects.

6.3.1 Primary Outcome Analysis

The primary outcome variable is the proportion of subjects experienced remission at week 16. 95% exact Clopper-Pearson confidence interval (CI) of the proportion of remission will be provided within each parent study treatment group and overall, as well as subgroup by anti-TNF agent use. Parent study treatment comparison will be performed using Fisher's exact test.

For the above primary analysis, subjects with a missing week 16 CDAI will be treated as not achieving remission. As a sensitivity analyses, the same analyses will be performed without imputation, i.e. subjects with missing week 16 CDAI will not be imputed, therefore it will be missing and excluded from analysis.

Logistic regression modeling will be implemented as additional exploratory analysis to assess relationships between the primary outcomes and putative effect modifiers. The putative effect modifiers include the following patient level biomarker assessment:

- Baseline serum inflammation marker: C-reactive protein (CRP ≥ 2.87 vs. < 2.87 mg/dL)
- Baseline stool inflammation marker: Fecal calprotectin (≥ 250 vs. < 250 mcg/g)
- Baseline SES-CD ≥ 6 , Fecal calprotectin ≥ 250 mcg/g or CRP ≥ 2.87 mg/dL: Yes vs. No

The logistic regression model includes remission at week 16 (yes/no) as a function of parent study treatment by baseline biomarker factor. The aim is to identify if the effect of each baseline biomarker factor has significant effect on remission outcome. The analysis will be performed to compare parent study treatment groups. Odds ratio of remission rate (parent study treatment RHB-104 vs. placebo) and 95% CI will be presented using a Forest plot for each baseline biomarker level. Similar plots will be provided for week 16 response and week 52 remissions.

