4.2 Dosage and Administration of Study Drug

The target dose of RHB-104 is 5 capsules administered bid. In order to reach this target with minimal adverse effects, subjects who received placebo during the RHB-104-01 study will be titrated up over the first 4 weeks of treatment, and the dose will remain stable thereafter. Subjects who received RHB-104 will continue to receive RHB-104. In order to maintain blinding in the RHB-104-01 study all subjects will receive 5 blinded capsules bid for the duration of the RHB-104-04 study as detailed below. The study drug will be taken with food. Subjects who fail dose escalation to 5 capsules bid will be considered treatment failures and withdrawn from the study.

Blinded bid Dose Titration and Maintenance Dosing in RHB-104-04 is

		RHB-104-04 START-UP KIT (Weeks 1-4)				MAINTENANCE KITS (Weeks 5-52)
		Weeks				
		1	2	3	4	5-52
BLINDED ACTIVE ARM (ACTIVE + ACTIVE)	RHB-104	Active Daily Dose (mg)				
	Clarithromycin	950mg	950mg	950mg	950mg	950mg
	Rifabutin	450mg	450mg	450mg	450mg	450mg
	Clofazimine	100mg	100mg	100mg	100mg	100mg

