5. ANALYSIS POPULATIONS

All subjects who signed informed consent will be included in the disposition table counts. The following populations will be used for data analysis.

The Intent-to-Treat (ITT) Population: The ITT population is defined as all subjects who are enrolled in this open-label study and signed the consent form. Efficacy endpoint analyses will be based on ITT population or specified otherwise.

The Safety Population (SAF): The safety population includes subjects who received any amount of study medication. The safety analyses will be based on the SAF population.

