6.1.3 Missing Data and Handling of Dropouts

All available outcome and safety data will be included in data listings and tabulations.

CDAI Missing Data:

The computation of CDAI requires 7 days of consecutive diary daily data. For subjects with CDAI diary data reported that is less than 7 days of data, the reported data will be standardized to 7 days by dividing the sum of CDAI score over the number of days of data by total number of days of reported data multiplied by 7. If less than 4 days of diary data is available, the subject will be categorized as a non-responder and the CDAI score will be considered missing. As specified in section 2.2, subjects with missing assessment will be assumed to not be in a state of remission/success for each scheduled visit (week 16, 26, or 52).

Handling of missing date information for AEs:

The term *missing date* refers to a completely missing date or to partial date where month or/and day or/and year is/are missing, e.g. missing month/day/year. Missing start and end dates will be imputed conservatively, i.e. missing values will be imputed in such a way that the duration of the AE is considered with the longest possible duration. The missing start date and end date of AE will be imputed for the purpose of defining treatment emergent adverse events (TEAE) and for assigning events to treatment periods using the following definitions:

(i) Adverse Event Start Date:

Event Missing Day: If Adverse event day is missing but month and year present, then impute the 1st of the month unless month and year are the same as first dose of study drug then impute day first day of dose.

Event Missing day and month – If adverse event day and month both are missing but year is present then impute 1st January unless year is the same as first dose date then impute day and month first dose day and month.

Completely missing – impute first dose date unless the end date suggests it could have started prior to this in which case impute the 1st January of the same year as the end date.

(ii) Adverse Event End Date:

Missing day – If AE day is missing but month and year is present then impute the last day of the month.

Missing day and month – If AE has missing day and month but year is present then impute 31st December.

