6.1.7 Determination of Sample Size

This study is anticipated to enroll 100 patients. With that number of patients, a two-sided 95% confidence interval (using the exact Clopper-Pearson method) will have a maximum width of 0.203 (i.e., +/- 10.15%) conservatively assuming the measure of interest has proportion of successes of 50%. This confidence interval will be narrower for any other possible observed proportion.

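### The only sensitivity analysis of week-16 remission drops failed-escalation subjects, whom the plan has already classed as treatment failures

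*SAP*

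**What the plan says.** SAP section 5 bases the efficacy analyses on an ITT population of "all subjects who are enrolled in this open-label study and signed the consent form". In the primary analysis of SAP 6.3.1, "subjects with a missing week 16 CDAI will be treated as not achieving remission". The same section then states one sensitivity analysis, which repeats the primary analyses on complete cases: "subjects with missing week 16 CDAI will not be imputed, therefore it will be missing and excluded from analysis". It appears as Table 14.2.1.3, which is labelled ITT. The repeated analyses include the exact intervals by parent group and overall, and Fisher's exact test between parent groups.

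Three other places bear on who has a missing week-16 CDAI:

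- SAP 4.2, and the dosage section of the protocol: "Subjects who fail dose escalation to 5 capsules bid will be considered treatment failures and withdrawn from the study".
- SAP 6.1.6 (and 2.2.1): subjects with new or increased treatment for Crohn's disease symptoms count as failures in remission and response analyses, but may stay on study drug and be assessed.
- SAP 6.1.3: with fewer than 4 diary days, "the subject will be categorized as a non-responder and the CDAI score will be considered missing".

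**The concern.** Failed escalation is an event, and the plan attaches an outcome to it. The active dose is raised over weeks 1 to 4. The schedule in SAP 4.1.1 has its first on-treatment CDAI at week 8 and no early-termination column. A subject withdrawn for failed escalation would therefore be expected to have no week-16 CDAI, and 6.3.1 removes that subject from the sensitivity denominator as if the outcome were unknown. The failure rule in 4.2 is not carried into 2.2.1, 6.1.6 or 6.3.1.

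Rescue leaves a smaller gap. A rescued subject with a week-16 CDAI stays in as a failure, but 6.3.1 does not say what happens to a rescued subject without one.

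At stake is how the one robustness check on the primary endpoint is read. Part of any rise over the primary rate would come from deleting known failures rather than from a different assumption about unknown outcomes. The parent-group comparison repeated on this set could also shift.

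**Working it through.** **The plan's own figure.** SAP 6.1.7 states that "This study is anticipated to enroll 100 patients" and gives a maximum interval width of 0.203. The exact Clopper-Pearson interval for 50/100 is 0.3983 to 0.6017, width 0.2034, so the figure is reproduced. (The Wald width would be 0.196.)

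**Inputs.** N = 100 is from SAP 6.1.7. The documents give no remission, missing-data or escalation-failure rates and no parent-group sizes. All the counts below are assumptions.

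**Formulas.** Let x be remitters, m subjects with missing week-16 CDAI, and f those among the m whom the plan already classes as treatment failures.

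- Primary: x / N
- Complete case, as planned: x / (N − m)
- Plan-defined failures kept, other missing excluded: x / (N − m + f)

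Every excluded subject was a non-remitter in the primary analysis, so x does not change. The planned analysis multiplies the primary rate by N / (N − m).

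**Overall rate, x = 25 (primary 25.0%, 95% interval 16.9 to 34.7).**

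| m | Complete case | Failures kept, f = half of m | Excess from dropping known failures |
|---|---|---|---|
| 10 | 25/90 = 27.8% | 25/95 = 26.3% | 1.5 points |
| 20 | 25/80 = 31.2% (21.3 to 42.6) | 25/90 = 27.8% (18.9 to 38.2) | 3.5 points |
| 30 | 25/70 = 35.7% | 25/85 = 29.4% | 6.3 points |

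The excess depends on f. With m = 20:

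- f = 0: no excess
- f = 2: 25/82 = 30.5%, an excess of 0.8 points
- f = 5: 25/85 = 29.4%
- f = 15: 25/95 = 26.3%

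**Parent groups (assumed 50 per group, 12 remitters each, so 24.0% vs 24.0% in the primary; former RHB-104 first).**

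| Missing | Complete case | Difference |
|---|---|---|
| 5 vs 5 | 12/45 = 26.7% vs 12/45 = 26.7% | 0 |
| 5 vs 10 | 26.7% vs 12/40 = 30.0% | −3.3 points |
| 5 vs 15 | 26.7% vs 12/35 = 34.3% | −7.6 points (Fisher p = 0.47) |
| 10 vs 5 | 30.0% vs 26.7% | +3.3 points |

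If 10 of the 15 missing in the third row are escalation failures and are kept, the former placebo rate is 12/45 = 26.7%, equal to the other group. The shift arises only when the missing shares differ, and its sign follows whichever group has more missing.

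**The case against.** The strongest objection is that the primary analysis already sets every missing subject to non-remission. Any alternative can then only raise the rate or leave it unchanged, multiple imputation and bounds included. This stands. A reader might infer that upward-only movement makes the complete-case analysis worthless as a robustness check. The documents do not support that: the direction follows from the conservative primary, and varying that assumption is legitimate for outcomes that are truly unknown.

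It can also be said that, under the primary rule, every missing subject has been assigned failure, so failed escalation is nothing special. That does not hold. Non-remission for a missing score is a convention about an unknown value, whereas 4.2 classifies a subject by something that happened. The argument does hold for subjects with fewer than 4 diary days. Their non-responder label in 6.1.3 is itself the missing-data convention, so their outcome is open to variation.

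Two further readings go too far:

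- **Escalation failures fall only in the former placebo group.** The rule in 4.2 is not limited by parent group, and both groups use blinded two-bottle start-up kits with the same changing bottle counts. A failed escalation could be recorded in either. That only former placebo subjects have their active dose raised makes an imbalance plausible, not established.
- **Withdrawal for lack of effect or adverse event is also a settled failure.** The plan does not define it so.

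It is also fair that the stated aim is to estimate a rate, that the protocol plans no formal between-group comparison (the SAP adds Fisher's test), and that the more conservative analysis is the primary. These points limit the importance of the gap but do not close it.

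**Conclusion.** The point holds as an inconsistency between SAP 4.2 and 6.3.1, with a related gap between 6.1.6 and 6.3.1. The sensitivity analysis treats as unknown some outcomes that the plan has already set, and this can raise the reported rate. Under the assumed 25% primary rate, with half of the missing being plan-defined failures, the excess is 1.5 to 6.3 points for 10 to 30 missing. It is under 1 point if only 2 of 20 missing are such failures. This rests on failed-escalation subjects having no week-16 CDAI, which the withdrawal rule and the visit schedule imply.

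A reader might conclude that the analysis will distort the parent-group comparison. The documents support only that it may do so, most plausibly by raising the former placebo rate more. The primary estimate is not affected. The change should be made, but the primary analysis does not depend on it.

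**What to change.** Reconcile SAP 4.2 and 6.1.6 with 6.3.1:

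- State in 6.3.1 that subjects the plan already defines as treatment failures remain non-remitters in every analysis. These are subjects with failed dose escalation and subjects with rescue, including rescued subjects with no week-16 CDAI.
- Vary only the other missing week-16 CDAIs, including those with fewer than 4 diary days. Use multiple imputation from baseline and week-8 CDAI and parent group, or best-case and worst-case bounds. The worst-case bound is the primary analysis.
- Tabulate missing week-16 CDAIs by reason and parent group. SAP 6.2.1 already summarises discontinuation reasons and week-16 completion by parent group, but not missing CDAIs as such.

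The cost is a few sentences in the SAP, a modified Table 14.2.1.3, one added tabulation and minor programming. No new data are needed. The drawback is a slightly less favourable sensitivity rate.
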